## Objectives

Primary Objective:	Outcome Measure:
To compare the mean change from baseline in glycosylated hemoglobin (HbA1c) achieved with dapagliflozin 5 mg or dapagliflozin 10 mg added to saxagliptin 5 mg plus metformin versus (vs.) placebo added to saxagliptin 5 mg plus metformin after 24 weeks of oral administration of double-blind treatment	Mean change from baseline in HbA1c at Week 24
Secondary Objective:	Outcome Measure:

To compare the mean change from baseline achieved with dapagliflozin 5 mg or dapagliflozin 10 mg added to saxagliptin 5 mg plus metformin vs. placebo added to saxagliptin 5 mg plus metformin after 24 weeks of oral administration of double-blind treatment in the following:

1) Fasting plasma glucose (FPG)

2) 2-hour PPG from a meal tolerance test (2-hour MTT)

3) Total body weight

To compare the proportion of subjects achieving a therapeutic glycemic response, defined as a HbA1c <math>< 7.0\%</math>, with dapagliflozin 5 mg or dapagliflozin 10 mg added to saxagliptin 5 mg plus metformin vs. placebo added to saxagliptin 5 mg plus metformin after 24 weeks of oral administration of double-blind treatment

	

Mean change from baseline in fasting plasma glucose (FPG) at Week 24

Mean change from baseline in 2-hour PPG during a meal tolerance test (2-hour MTT) at Week 24

Mean change from baseline in Total body weight at Week 24

Percent of subjects achieving a therapeutic glycemic response, defined as a HbA1c <math>< 7.0\%</math> at Week 24

Safety Objective:	Outcome Measure:

To evaluate the safety and tolerability of therapy with dapagliflozin 5 mg or dapagliflozin 10 mg added to saxagliptin 5 mg plus metformin vs. placebo added to saxagliptin 5 mg plus metformin after 24 weeks of oral administration of double-blind treatment
	
 
Adverse Events (AEs) /Serious Adverse Events (SAEs)
 
AEs of special interest (AESI)
 
Clinical laboratory tests
 
Physical examination
 
ECG
 
Vital signs
 


Exploratory Objective:
 
 
To assess the percent of subjects who require rescue or discontinue study treatment for lack of efficacy with dapagliflozin 5 mg or dapagliflozin 10 mg added to saxagliptin 5 mg plus metformin vs. placebo added to saxagliptin 5 mg plus metformin up to 24 weeks of oral administration of double-blind treatment
 
To assess the time to glycemic rescue or discontinuation for lack of efficacy with dapagliflozin 5 mg or dapagliflozin 10 mg added to saxagliptin 5 mg plus metformin vs. placebo added to saxagliptin 5 mg plus metformin during the short-term double-blind period
 
To assess the mean change from baseline in area under the curve (AUC) of glucose obtained during a MTT with dapagliflozin 5 mg or dapagliflozin 10 mg added to saxagliptin 5 mg plus metformin vs. placebo added to saxagliptin 5 mg plus metformin after 24 weeks of oral administration of double-blind treatment
 
To assess the mean percent change from baseline in fasting serum lipids (Total-C, LDL-C, HDL-C, TG) with dapagliflozin 5 mg or dapagliflozin 10 mg added to saxagliptin 5 mg plus metformin vs. placebo added to saxagliptin 5 mg plus metformin after 24 weeks of oral administration of double-blind treatment
 
	
Outcome Measure:
 
 
Percent of subjects who require glycemic rescue or discontinue study treatment for lack of efficacy up to Week 24
 
Time to glycemic rescue or discontinuation for lack of efficacy in the double-blind treatment period
 
Mean change from baseline in AUC of glucose obtained during a MTT at Week 24
 
Mean percent change from baseline in fasting lipids (Total-C, LDL-C, HDL-C, TG) at Week 24
 

### Target subject population

Approximately 342 subjects aged  $\geq 18$  years who have type 2 diabetes mellitus (T2DM) with inadequate glycemic control (defined as a central laboratory HbA1c  $\geq 7.0$  and  $\leq 10.5\%$  for both strata obtained at the week -2 visit) taking stable metformin IR/XR therapy and open-label saxagliptin 5 mg will be randomized to 1 of 3 treatment groups in a 1:1:1 ratio.

### **Duration of treatment**

Study duration will be at least 42 weeks (Stratum A) or 34 weeks (Stratum B), including a 2-week screening period, a 16-week (Stratum A) or 8-week (Stratum B) lead-in period, and a 24-week double-blind treatment period.

### **Investigational product, dosage and mode of administration**

#### **Dapagliflozin and dapagliflozin placebo to match**

Dapagliflozin 5mg tablets, dapagliflozin 10 mg tablets and dapagliflozin 5mg or 10mg placebo to match tablets, administered orally once daily for the 24-week double-blind treatment period.

### **Other Treatments**

**Saxagliptin:** Saxagliptin 5 mg tablets, administered orally once daily for the lead-in period and the 24-week double-blind treatment period.

**Metformin:** Throughout the study duration, subjects should continue to adhere to the same metformin treatment regimen as they were using at study entry. Metformin should be administered and stored according to product and country specific labelling.

**Rescue therapy:** Subjects who require rescue therapy should receive standard of care treatment (insulin or any other antidiabetic agents except Glucagon-like peptide-1 (GLP-1) analogues, other DPP-4 inhibitors and/or SGLT2 inhibitors or metformin).

### **Statistical methods**

The primary endpoint (mean change from baseline in HbA1c at Week 24) will be assessed comparing dapagliflozin 5 mg or dapagliflozin 10 mg added to saxagliptin 5 mg plus metformin vs. placebo added to saxagliptin 5 mg plus metformin. Statistical significance of the primary endpoint will be claimed if the p-values for dapagliflozin 10 mg + saxagliptin 5 mg + metformin vs. placebo + saxagliptin 5 mg + metformin comparison is significant at the 2-sided, 0.05 significance level. As the success of primary endpoint on the dapagliflozin 5 mg + saxagliptin 5 mg + metformin vs. placebo + saxagliptin 5 mg + metformin comparison is important, the sample size is planned to provide at least 90% power for primary endpoint on both comparisons.

With 108 subjects per treatment group with post-baseline assessment, there is 95% power to detect -0.5% difference for dapagliflozin 10 mg + saxagliptin 5 mg + metformin vs. placebo + saxagliptin 5 mg + metformin comparison, assuming a standard deviation (SD) of 1.0% with a 2-sided significance level of 0.05. This sample size will also provide at least 90% power to detect -0.5% difference for both dapagliflozin 10 mg + saxagliptin 5 mg + metformin vs. placebo + saxagliptin 5 mg + metformin and dapagliflozin 5 mg + saxagliptin 5 mg + metformin vs. placebo + saxagliptin 5 mg + metformin comparisons, assuming a SD of 1.0% with a 2-sided significance level of 0.05.

Assuming that 5% of subjects would not have a post-baseline assessment, a total of approximately 342 subjects (114 subjects per treatment arm, with about 91 subjects from China and about 23 subjects from other countries/regions) need to be randomized. In other words, Chinese subjects will constitute about 80% of the total number of subjects. This study includes two strata, based on prior antihyperglycemic treatment. Subjects with HbA1c uncontrolled on a stable dose of metformin ( $\geq 1500$  mg/day or a maximal tolerated dose) are enrolled into a 16-week open-label treatment period (Stratum A), adding saxagliptin 5 mg to metformin. Subjects with HbA1c uncontrolled on a stable dose of metformin ( $\geq 1500$  mg/day or a maximal tolerated dose) AND a maximal dose of a DPP-4 inhibitor are enrolled into an 8-week open-label treatment period (Stratum B), following treatment with saxagliptin 5 mg plus metformin. Subjects from two strata who remain uncontrolled HbA1C are subsequently randomized.

It is desired to have approximately 33% of the randomized subjects coming from Stratum B. In addition, enrolment of subjects with HbA1c  $\geq 8.0\%$  and  $< 9.0\%$  (Stratum A) and subjects with HbA1c  $\geq 7.5\%$  and  $\leq 8.5\%$  (Stratum B) into the open-label treatment period will be limited to approximately 171 subjects (about 50% of the randomized subjects number in each stratum).

About 40% (Stratum A) and 6.5% (Stratum B) of subjects are expected to be discontinued due to severe lack of glycaemic control (defined as FPG  $> 270$  mg/dL at Week -10 or Week -2 in Stratum A and Week -2 only in Stratum B) during the open-label treatment period. In addition, it is expected that 50% of screened subjects will fail to meet eligible criteria for open-label treatment of each stratum. This leads to a total of 1004 subjects to be screened, with a targeted 380 subjects in Stratum A and 122 subjects in Stratum B to enter the open-label treatment period.

The primary efficacy analysis will compare the change from baseline in HbA1c at Week 24 for dapagliflozin 5 mg or dapagliflozin 10 mg + saxagliptin 5 mg + metformin treatment groups and the placebo + saxagliptin 5 mg + metformin group. Each comparison will be performed at the 0.05 significance level (2-sided) using the hierarchical testing specified in Section 8.1. This maintains the familywise type I error rate at 0.05.

The primary efficacy analysis of HbA1c at week 24 will be performed using a mixed-model repeated-measures (MMRM) model with terms for treatment group, stratum, baseline HbA1c value, time, the interaction of treatment and time, and the interaction of baseline HbA1c value and time in the model, including observations prior to rescue and study treatment discontinuation only, without explicitly imputing missing data. An unstructured matrix for the within-subject error variance-covariance will be used. The denominator degrees of freedom will be calculated according to the Kenward-Roger method. In case of non-convergence of the preferred model or memory space issue, the back-up models will be used (e.g. calculate the denominator degrees of freedom using other method like Satterthwaite approximation, use other covariance matrix like Toeplitz, AR (1), use simpler models, and etc.). Details will be documented in statistical analysis plan (SAP). Point estimates and 95% confidence intervals

Clinical Study Protocol  
Drug Substance Dapagliflozin  
Study Code D1683C00008  
Edition Number 5.0  
Date 14 Feb 2019

will be calculated for the adjusted mean changes within each treatment group as well as for the differences in adjusted mean changes between treatment groups.

Intent-to-treat (ITT) analysis set will be used for the primary efficacy analysis.

The same MMRM approach used for HbA1c evaluation will also be used for the analysis of FPG and total body weight. Point estimates and 95% confidence intervals will be calculated for the adjusted mean changes within each treatment group as well as for the differences in adjusted mean changes between treatment groups.

The analysis of covariance (ANCOVA) using last observation carried forward (LOCF) methodology with terms for treatment group, stratum, and baseline 2-hour postprandial plasma glucose (PPG) value will be used to evaluate 2-hour PPG. Point estimates and 95% confidence intervals will be calculated for the adjusted mean changes at Week 24 within each treatment group as well as for the differences in adjusted mean changes between treatment groups.

The proportion of subjects achieving a therapeutic glycaemic response (defined as HbA1c < 7.0%) at Week 24 (LOCF) will be summarized by treatment group and compared between treatment groups using the logistic regression based on methodology of Zhang et al (Zhang 2008) and Tsiatis et al (Tsiatis 2008) with adjustment for baseline HbA1c and stratum. Point estimates and 95% confidence intervals will be calculated for the response rate within each treatment group as well as the difference in response rates between treatment groups.

Safety analyses for the double-blind treatment period will be performed using the safety analysis set, including data after rescue. Safety analyses will include, where appropriate, descriptive statistics, counts, and percentages for AEs and other safety measures. No formal statistical tests will be performed for safety endpoints. Selected safety and efficacy analyses will be performed for the open-label treatment period using the open-label treated subjects analysis set.

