#### **6.3.6 Adverse events based on examinations and tests**

The results from protocol mandated laboratory tests and vital signs will be summarised in the clinical study report (CSR). Deterioration as compared to baseline in protocol-mandated laboratory values, vital signs and other safety variables should therefore only be reported as

AEs if they fulfil any of the SAE criteria or are the reason for discontinuation of treatment with the IP.

If deterioration in a laboratory value/vital sign is associated with clinical signs and symptoms, the sign or symptom will be reported as an AE and the associated laboratory result/vital sign will be considered as additional information. Wherever possible the reporting investigator uses the clinical, rather than the laboratory term (e.g., anaemia versus low haemoglobin value). In the absence of clinical signs or symptoms, clinically relevant deteriorations in non-mandated parameters should be reported as AE(s).

Any new or aggravated clinically relevant abnormal medical finding at a physical examination as compared with the baseline assessment will be reported as an AE.

For instructions how to handle AE based on ECG see section 5.2.3 and safety analyses for ECG recording see section 8.5.7.

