#### **8.5.7 Safety analysis**

Safety analyses for the double-blind treatment period will be performed using the Safety analysis set, including data after rescue. Safety analyses will include, where appropriate, descriptive statistics, counts and percentages for AEs and other safety measures. No formal statistical tests will be performed.

The number and percent of subjects with at least one AE will be summarized for each treatment group, including summaries of AEs, SAEs, AEs leading to discontinuation, and AEs of special interest. Summaries will include the number of subjects with events by specified system organ classes and preferred terms.

Additionally, the incidence of AEs and frequency of recurring AEs will be summarized for each treatment group for both frequent events and for selected AEs of special interest.

Values and changes from baseline at each scheduled time point for clinical laboratory parameters and vital signs, including seated BP and HR, will be summarized by treatment group using descriptive statistics. The normality/abnormality of ECG tracings, as determined by the investigator, will be summarized by shift tables overall and by ECG tracing at baseline. The number and percent of subjects with laboratory values meeting marked abnormality criteria will be summarized for each treatment group. Other safety assessments including Scr and eGFR by MDRD, will be summarized by treatment group using descriptive statistics of values and changes from baseline at each scheduled time point.

Additional analyses for AEs and laboratory marked abnormalities may be performed excluding data after rescue and study treatment discontinuation. The primary analyses of events of hypoglycaemia will be performed excluding data after rescue and study treatment discontinuation.

Selected safety analyses will be performed for the open-label treatment period using the Open-label treated subjects analysis set.

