### **4.4 Early termination analyses**

On Jun 30, 2020 AstraZeneca decided to stop commercialization of QTERNMet/Qtrilmel and to withdraw all active licenses, for business reasons. DS-NAVIGATION will be closed without recruiting subjects in China and patients recruited from Thailand and Vietnam will complete the study.

Therefore, the planned analyses in this study will be conducted over all data available. To support the synopsis format CSR, the following analysis will be performed:

- Summaries of subject disposition, summaries in the Enrolled subjects set and Open-label treated subjects analysis set, as described in Section 4.2.1. Subject disposition will also be listed.
- Summary of analysis set, defined in Section 2.1.
- Demographic and baseline characteristics as described in Section 4.2.2 and Section 4.2.2.1.
- An overall summary of adverse events at subject level, including TEAEs, TESAEs, death, hypoglycaemia, severe events, treatment-related events, events leading to the discontinuation of study medication, events leading to death will be presented for open-label treatment period and double-blind treatment period. TEAEs will also be summarised by SOC and PT in open-label and double-blind treatment. TESAEs will be summarised by SOC and PT in the double-blind period only. AEs and SAEs will also be listed.
- Important protocol deviations, observed HbA1c data, and marked abnormalities by test will be listed.

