## **5. INTERIM ANALYSES (NOT APPLICABLE)**

## **6. CHANGES OF ANALYSIS FROM PROTOCOL**

Due to early termination for business reasons, the analyses planned in this study will not be performed as planned, all but the analyses in Section 4.4.

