### Conventional (CV) Units:

Clinical Laboratory variables	Units	Marked Abnormality Criteria	
		Low	High
Hematology			
HCT males/females	%	< 20.0%	> 55.0%
HCT males/females	%		> 60.0%
Hemoglobin males/females	g/dL	< 6 g/dL	> 18 g/dL
Hemoglobin males/females	g/dL		> 20 g/dL
Blood Chemistry			
Total protein	g/dL		> 10 g/dL
ALP	U/L		> 3X ULN
ALT	U/L		> 3X ULN
AST	U/L		> 3X ULN
ALT	U/L		> 5X ULN

Clinical Laboratory variables	Units	Marked Abnormality Criteria	
		Low	High
AST	U/L		> 5X ULN
ALT	U/L		> 10X ULN
AST	U/L		> 10X ULN
ALT	U/L		> 20X ULN
AST	U/L		> 20X ULN
Total Bilirubin	mg/dL		> 2X ULN if PreRx ≤ ULN; > 3X ULN if PreRx > ULN
Glucose, Plasma Unspecified	mg/dL	< 54 mg/dL	> 350 mg/dL
Na (Sodium)	mEq/L	< 130 mEq/L	> 150 mEq/L
Na (Sodium)	mEq/L	< 120 mEq/L	
K (Potassium)	mEq/L	≤ 2.5 mEq/L	≥ 6.0 mEq/L
HCO3 (Bicarbonate)	mEq/L	≤ 13 mEq/L	
Creatinine	mg/dL		≥ 1.5X PreRx CREAT
Creatinine	mg/dL		≥ 2.5 mg/dL
CK (Creatine Kinase) 	U/L		> 5X ULN
CK (Creatine Kinase) 	U/L		> 10X ULN
Calcium	mg/dL	< 7.5 mg/dL	≥ 1 mg/dL from ULN and ≥ 0.5 mg/dL from PreRx CA
Magnesium	mEq/L	< 1 mEq/L	> 4 mEq/L
PO4 (Phosphate)	mg/dL	Age 17-65: ≤ 1.8mg/dL Age ≥ 66: ≤ 2.1 mg/dL	Age 17-65: ≥ 5.6 mg/dL Age ≥ 66: ≥ 5.1 mg/dL
Urine			
UACR (Urinary Albumin to Creatinine Ratio)	mg/g		> 1800 mg/g

For creatine kinase, ULN: Males (<65 years=250 U/L; ≥65 years=203 U/L), Females (<65 years=170 U/L; ≥65 years=160 U/L)

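### SAP 4.4 drops vital signs and creatinine/eGFR by visit, so non-serious, symptom-free changes that protocol 6.3.6 keeps out of AE reporting can appear in no output

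*Protocol*

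**What the plan says.** The protocol's safety objective (Synopsis and Section 2.3) names AEs/SAEs, AESI, clinical laboratory tests, physical examination, ECG and vital signs as outcome measures. The Synopsis says "Safety analyses will include, where appropriate, descriptive statistics, counts, and percentages for AEs and other safety measures". Protocol 8.5.7 is more specific: laboratory and vital-sign values and changes are summarised at each scheduled time point, and "Other safety assessments including Scr and eGFR by MDRD, will be summarized by treatment group". SAP 4.2.5.3 and 4.2.5.4 repeat this for the double-blind period.

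Protocol 6.3.6 builds an AE-reporting rule on those summaries. It first states that "The results from protocol mandated laboratory tests and vital signs will be summarised in the clinical study report (CSR". It then says that deterioration in "laboratory values, vital signs and other safety variables should therefore only be reported as" AEs when an SAE criterion is met or the change is the reason for stopping IP. If there are symptoms, the symptom is the AE and the measurement is supporting information.

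After the decision to close the trial, SAP 4.4 sets out a reduced set for a synopsis-format CSR: disposition, analysis sets, demographics and baseline, an overall AE summary, TEAEs by SOC and PT in both periods, double-blind TESAEs, and AE and SAE listings. It ends with "Important protocol deviations, observed HbA1c data, and marked abnormalities by test will be listed". SAP Section 6 states that "the analyses planned in this study will not be performed as planned, all but the analyses in Section 4.4".

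**The concern.** The rule in protocol 6.3.6 is reasonable only while the summaries it relies on exist. SAP 4.4 withdraws them, but the AE data were to be collected under the restrictive rule, so AE tables cannot recover what sites were told to leave out.

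The measures affected are ones where the protocol itself anticipates an effect. Section 1.2 describes a mild diuretic effect with the potential to lower blood pressure. The note in Section 3.9.1 describes an eGFR reduction of up to 10% at initiation, in general reversible. Volume depletion and renal impairment are both AESI categories (Section 6.1.1). At stake is whether the CSR shows any post-baseline blood pressure, heart rate or moderate renal change, by arm or by subject, beyond what qualified as an AE.

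**Working it through.** The point turns on no stated figure, so the first step sets planned outputs beside retained ones.

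| Measure | Planned | Kept in SAP 4.4 | Other route to output |
|---|---|---|---|
| SBP, DBP, heart rate | Values and changes by visit (protocol 8.5.7, SAP 4.2.5.4) | Nothing; Appendix 2 has no vital-sign criterion | AE if serious or IP-stopping; accompanying symptom as AE |
| Creatinine | Values and changes by visit (SAP 4.2.5.3) | Listed only when a marked abnormality | Same |
| eGFR | Values and changes by visit (SAP 4.2.5.3) | Nothing; Appendix 2 has no eGFR criterion | Same, plus the sustained-fall route in step 4 |
| AESI | By category and PT (SAP 4.2.5.1) | TEAEs by SOC/PT, AE listing, hypoglycaemia in the overall summary | Already AEs |
| ECG, physical examination | ECG shift table (SAP 4.2.5.5) | No separate output | Clinically significant ECG abnormalities and new or aggravated clinically relevant examination findings are AEs (protocol 5.2.3, 6.3.6) |

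The complete laboratory listing mentioned in SAP 4.2.5.3 is not carried into 4.4. The gap is thus confined to vital signs and laboratory values.

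The second step asks how much renal change the marked-abnormality listing would show. Inputs: MDRD creatinine exponent −1.154 (protocol 5.2.1.3); creatinine criteria "≥ 1.5X PreRx CREAT" and at least 2.5 mg/dL (SAP Appendix 2); entry excludes creatinine of 1.5 mg/dL or more in men and 1.4 or more in women, and eGFR below 60 (protocol 3.2). Within a subject, with age essentially unchanged, eGFR ratio = (creatinine ratio)^−1.154.

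1. **At the criterion.** 1.5^−1.154 = 0.626, an eGFR fall of 37.4%.
2. **Absolute criterion.** If baseline is within the entry limits, 1.5 × 1.5 = 2.25 mg/dL in men and 1.5 × 1.4 = 2.10 mg/dL in women. Both are under 2.5, so the relative criterion is reached first and the absolute one adds little.
3. **Smaller falls.** The 10% fall named in the protocol needs a creatinine ratio of 0.9^(−1/1.154) = 1.096. To reach 59.9 mL/min/1.73 m² from 75 needs (59.9/75)^(−1/1.154) = 1.22; from 90 it needs 1.42. All are below 1.5. Since 60/0.626 = 95.8, a subject starting anywhere from 60 to about 95 can drop below 60 without a creatinine marked abnormality.
4. **Sustained falls.** Protocol 3.9.1 requires IP to stop when eGFR is below 60 for 16 weeks. Stopping for that reason makes the fall an AE. Failing to stop is important deviation 3.8 in SAP Appendix 1, and 4.4 lists important deviations. On the protocol's 16 weeks, a fall first seen at Week 6 can qualify (24 − 6 = 18 weeks). One first seen at the Week 12 visit or later cannot qualify within the double-blind period (24 − 12 = 12 weeks).

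**The case against.** The strongest reply is that this is a declared reduction in scope. The trial was closed for business reasons without recruiting in China, 4.4 is written for a synopsis CSR, and Section 6 and the SAP amendment history disclose the change. The Synopsis sentence is general and qualified by its own "where appropriate" clause. That stands as far as it goes, but 6.3.6 carries no such qualifier, and its stated reason for restricting AE reporting no longer holds.

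Four stronger readings are tempting, and the documents do not support them.

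- **That laboratory and vital-sign deterioration vanishes altogether.** Serious, symptomatic or IP-stopping changes are still captured as AEs. Marked abnormalities are still listed, covering creatinine, potassium, sodium, bicarbonate, haematocrit, liver tests and UACR among others.
- **That AESI go unreported.** They are AEs and remain in the PT tables and listings; only the grouping by category is lost.
- **That any fall of eGFR below 60 is hidden.** A fall sustained for 16 weeks has the two routes in step 4. Transient, later or smaller falls do not.
- **That the open-label period loses the same output.** The full SAP planned these change summaries for the double-blind period only.

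It can also be said that 4.4 itself contains a sentence under which the planned analyses are to be run on whatever data are available, so nothing is dropped. That conflicts with Section 6 and with the limited list that follows it. The exclusive reading is the more natural one, but the text is ambiguous. Sites and the sponsor also still receive eGFR results during the study, so the point concerns reporting, not monitoring of individual subjects.

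**Conclusion.** The concern holds in a limited form. With protocol 6.3.6, SAP 4.4 and SAP Section 6 followed as written, non-serious, symptom-free vital-sign changes that do not stop IP appear in no table or listing. The same is true of such renal changes while creatinine stays below both marked-abnormality criteria, in practice an eGFR fall of up to about 37%, apart from the sustained fall below 60 described above. Vital signs are the clearer loss, because no threshold brings them back.

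A reader might go further and infer that the safety objective cannot be answered. That is too strong: AE, SAE, death and marked-abnormality output remains. What is missing is the descriptive part for two named outcome measures.

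This rests on reading Section 6 as exclusive, on double-blind baseline creatinine lying within the entry limits, and on sites following 6.3.6. The number of subjects affected is unknown. The plan's figure outside China is about 23 per arm, or 3 × 23 = 69, but that is a planning number and the documents do not give enrolment at closure. The change is worth making as a cheap improvement.

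**What to change.** Add to SAP 4.4, for the double-blind period by treatment group, at least a listing of SBP, DBP, heart rate, creatinine and eGFR values with change from baseline. The by-visit summaries already specified in SAP 4.2.5.3 and 4.2.5.4 would serve equally well. An AESI category table, as in SAP 4.2.5.1, is optional because the events are already shown by PT.

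Reword the 4.4 sentence about running the planned analyses on all available data so that it agrees with Section 6. While Appendix 1 is open, reconcile deviation 3.8, which gives 12 to 16 weeks, with the 16 weeks in protocol 3.9.1.

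The cost is a few lines of SAP text and a handful of outputs that are already specified, on data already scheduled for collection, with a slightly longer synopsis CSR as the only drawback.
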